The early work from [name] (see the preliminary data section) showed HF patients derived increase muscle strength from training affects. Likewise, in a small trial Magnusson et al. (63) 11 HF patients were randomized into two groups, knee extensor strength training and/or endurance training, each 3 days/week for 8 weeks. After training, overall exercise tolerance increased from 99 to 114 watts ($p<0.05$). Peak dynamic knee extensor work rate showed the greatest increase in association with endurance training (40%, $p<0.01$). Capillary per fiber ratio of the vastus lateralis was also greater in the endurance trained legs ($p<0.05$). However, the dynamic and isometric strength and cross-sectional area of the quadriceps femoris were relatively greater with strength training. The study is most relevant in demonstrating that exercise effects vary depending on whether the training is strength or aerobic-based.

Selig et al. (64) demonstrated that moderate-intensity strength training positively effects muscular strength and endurance, peak VO_2 , forearm blood flow (FBF), and heart rate variability (HRV) in 39 HF patients. Patients underwent tests for strength and endurance of the knee and elbow extensors and flexors, peak VO_2 , HRV, FBF at rest, and FBF activated by forearm exercise or limb ischemia. Patients were then randomized to 3 months of resistance training vs. endurance training vs. usual care, after which they underwent repeat assessments. Strength increased in the resistance training group by 30% ($p<.01$), vs. 21% in the endurance group ($p<.01$) vs. almost unchanged in the usual care (strength $p<.005$, endurance $p<.003$ in the strength

training group vs. the usual care). Peak VO_2 improved in the resistance training group by 15% ($p < .01$), but decreased by 18% ($p < .05$) in the usual care group ($p < .001$ strength training vs. usual care).

Overall, these studies indicate that strength training increases skeletal muscle hypertrophy and force production, but also translates into aerobic benefits, as increased strength essentially enables patients to sustain aerobic activity for longer periods before fatiguing (65).

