Combined Aerobic and Strength Training: Understanding the benefits of aerobic training versus strength training leads many to believe that a combination of the two may be the most beneficial form of exercise for HF patients. The overall rationale is to incorporate benefits of each, i.e., endothelial, autonomic, neurohormonal, and anti-inflammatory effects, in combination with direct stimulus for cell growth and anti-atrophic benefit. In the study mentioned above, Magnussen et al (63) demonstrated synergy when endurance and strength exercise training were combined. Likewise, Maiorana et al. (66) utilized an 8 week exercise intervention consisting of circuit weight training (CWT) for 13 male HF patients. The CWT sessions were held 3 days per week for one hour, involving a combination of treadmill walking, cycle ergometry, and resistance weight training. Results of the study demonstrated that CWT improved cardiorespiratory fitness and muscular strength in patients with HF. Significant improvements were seen in muscle strength (392 to 462 kg $P = 0.001$), peak VO_2 (19.5 ± 1.2 vs. $22.0 \pm 1.5 \text{ mL O}_2 \cdot \text{kg}^{-1} \cdot \text{min}^{-1}$, $p < 0.01$), RPP, and submaximal heart rate after training (121 ± 3 vs. 134 ± 5 beats/min, $P < 0.01$). The study concluded that resistance training combined with aerobic training lead to beneficial improvements in strength and functional capacity for HF patients.

In addition to physiological benefits, Radzewitz et al. (67) demonstrated that combined aerobic and strength training lead to significant improvements in quality of life for male and female HF patients. The training program lasted 4 weeks and consisted of strength training (2-3 times per week), cycle ergometry (3 times per week), and a 6MWT as a training mode (2 times per week). The study results showed significant improvements in cardiopulmonary exercise testing (CPX)-based assessments as well as in quality of life.

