An implicit aspect of this work is that it attests to the first-class research infrastructure we have been able to organize in the last 3 years. We have developed a highly successful program and research facility at the VA Boston Healthcare System (VABHS), facilitating recruitment, functional assessments, muscle biopsies, dual-emission X-ray absorptiometry (DXA), exercise training, and echocardiography, as well as tissue storage, data storage, and data analysis. We have become a substantial resource within the VABHS research program, growing our own program and work, but also enriching other investigators whose work entails exercise assessment, exercise training, and exercise science.

- *Phase I:* We compared functional capacity between HF and controls, evaluating CPX indices, strength testing, body composition, and basic clinical measures. We showed that key aerobic and strength indices were significantly decreased in HF patients (peak VO_2 [15.4±4.2 vs. 23.4±6.6, $\text{mLO}_2\cdot\text{kg}^{-1}\cdot\text{min}^{-1}$ p<0.0001], VAT [10.9±2.1 vs. 14.4±4.0 $\text{mLO}_2\cdot\text{kg}^{-1}\cdot\text{min}^{-1}$, p<0.0001], VE/V CO_2 slope [35.7±10.6 vs. 29.1±4.6, p<0.0001], 1RM [154.8±52.0 vs. 195.3±56.8kg, p<0.01], power [226.4±99.2 vs. 313.3±130.6 watts, p<0.01]), and the 6MWT distance (388.8±114.9 vs. 536.5±182.7 meters, p<0.001) reflecting the pathophysiological-associated functional decrements in an HF population.

Table 1

Phase I. Evolving scientific insights regarding functional measures and body composition, in HF vs. controls.

Title	Summary	Venue
Comparing physical and functional measures in HF patients and healthy controls	While age correlated inversely to all functional variables in HF and controls, differences between groups were evident in relation to peak VO_2 , leg endurance, 6MWT, and the Duke Activity Status Index (DASI). While Peak VO_2 correlated with leg endurance, DASI did not correlate with physical function measures.	American College of Sports Medicine, 2011
The Influence of Functional Parameters on Quality of Life in Systolic HF Patients	The Kansas City Cardiomyopathy Questionnaire (KCCQ) correlated with aerobic indices in HF patients but not strength parameters. Aerobic capacity may be a key determinant in quality of life in HF patients.	Society of Behavioral Medicine, 2011

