	Visit 2 (within one week of visit 1)	Skeletal muscle biopsy; Serology and DXA scan Randomization
	Visit 3 (2-3 days after visit 2) (VABHS only)	Reassessment of biopsy site
Exercise Training	Visits 3/4-38/39	Exercise training sessions (3X/weekly; 60 minutes; 12 weeks)
Post assessment	Visit 39/40-41/43	Post-exercise assessment battery and additional group of assessments completed at visits 1 to 2/3

Table 5: Expansion to a Multi-Site Trial

	Recruitment goals	Exercise arms
VAMC Pittsburgh	100	Aerobic (35), Combined aerobic-strength (30 enrollees), IMT (35 enrollees)
VAMC Boston	50	Aerobic (25 enrollees); IMT (25 enrollees)

Total: 150 HF patients: Aerobic—60; IMT—60; Combined—30;

Study Population

• ***Study Population:*** 150 male and female systolic HF patients with mild-moderate symptoms while on optimal medical therapy will be enrolled. This target will allow for adequate power to address the study objectives even after accounting for a 20% drop-out rate due to attrition and/or suboptimal tissue samples for genetic analysis. Given the expansion to two campuses, and the variation in randomization at each site, the overall proportions of patients enrolled will vary from the original study design but still provide a sound statistical foundation for the anticipated analyses (see statistics section below).

• HF diagnosis will be contingent on a previous hospitalization for HF or physician assessment of HF associated. Each candidate will be examined at the time of enrollment by a cardiologist to ensure that he/she is clinically stable.

• ***Inclusion Criteria:***

- NYHA class II or III for the previous three months despite a minimum of 6 weeks of optimal treatment

- Age \geq 50 years

- Left ventricular EF (LVEF) (by echocardiogram or radionucleotide imaging study within 12 months of enrollment).

- Optimal therapy according to AHA/ACC and HFSA HF guidelines, including treatment with ACEI and beta-blocker therapy (for at least 6 weeks), or have documented reason for variation, including medication intolerance, contraindication, patient preference, or personal physician's judgment.

✓ Patients using aspirin (ASA) will be eligible, but asked to hold the medication for 48 hours prior to biopsy. This technique has previously been used with consistent safety. Patients will also be asked to avoid non-steroidal anti-inflammatory medications (NSAIDs) for 48 hours prior to the biopsy.

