a) *Aerobic vs. Strength vs. Aerobic-Strength regimens will be compared to one another b) Inspiratory Training will be compared to Aerobic-Strength:* In this aim, we compare the combined aerobic-strength training regimen to the single-therapy regimens of aerobic training and strength training, as well as the inspiratory training regimen. These comparisons will be made with changes in the functional outcomes (peak VO₂, 1RM) from baseline as the continuous outcome measures in separate models and training regimen as the categorical predictor in a general linear model, with the following factors considered as potential confounder variables: age, sex, and comorbidities. To limit the type I error rate, only the pre-planned comparisons of the combined aerobic-strength training to the other regimens will be considered. In addition, secondary analyses will consider the following aerobic, strength and inspiratory variables as outcome variables in similar analyses to those outlined above: 6MWT, sit-to-stand, and hand grip strength.

- **Aim 2. To assess gene expression and skeletal muscle perfusion in relation to the different training regimens:** In this aim, we examine the change from baseline to post-exercise regimen in the expression of proteolytic (FoxO and Ubiquitin) and anti-proteolysis (IGF-1 and PGC-1 α) genes as predictors of the change in functional outcomes (peak VO₂, 1RM) over the same period. Separate general linear models for each functional outcome will be performed with gene expression changes as the primary predictor and the following variables considered as potential confounders: age, sex, and comorbidities. As above, a 10% rule for introducing confounding variables and the transformation of outcome variables to deal with regression assumption violations will be considered.

Treatment regimens will also be categorized as those with and without direct skeletal muscle stimulation and this categorical variable will be considered as a predictor of a change in the expression of proteolytic and anti-proteolysis genes in general linear models in a similar fashion to that described above. In addition, similar general linear models will be used with changes in skeletal muscle perfusion as a continuous outcome and aerobic and inspiratory training vs. strength-only training as a categorical predictor with similar potential confounders as noted above.

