Secondary analyses will include assessment of the relative impact of changes in skeletal gene expression vs. changes in perfusion dynamics as predictors of changes in function and quality of life as outcomes. Measures of changes from baseline in serum inflammation, cytokines, and adipokines, and effects of muscle histology will be included as covariates in these analyses. General linear models will be used (outlined above).

Sample size/Power: In this study, we plan to recruit 210 individuals and assign them to one of 4 treatment arms, i.e., randomized between aerobic, aerobic strength, and IMT in VAPHS and between aerobic and inspiratory muscle training in Boston. Sample size calculations are based on 20% attrition over the course of the study. In general, a sample size of 40 per group, using a t-test of independent samples as a simplified model, results in an effect size of 0.64 SD units for 80% power, using a two-sided alpha of 5%.

- **Aim 1:** For this aim, we present calculations for detecting differences in peak VO₂. Previous work by Becker (108) shows a $2.1 \text{ mL O}_2 \cdot \text{kg}^{-1} \cdot \text{min}^{-1}$ change in peak VO₂ in a 6 month aerobic-strength training regimen. Similarly, Tyne-Lenne, et al. shows a $1.1 \text{ mL O}_2 \cdot \text{kg}^{-1} \cdot \text{min}^{-1}$ change in a strength-only regimen (109), HF-ACTION (85) shows a $0.6 \text{ mL O}_2 \cdot \text{kg}^{-1} \cdot \text{min}^{-1}$ change in an aerobic regimen and the IMT trial by Dall'Ago et al. (12) shows a $4 \text{ mL O}_2 \cdot \text{kg}^{-1} \cdot \text{min}^{-1}$ change with inspiratory training. Standard deviations [SD] of the change in peak VO₂ over an exercise regimen are not directly available but using interquartile range values from the largest study [HF-ACTION, n=1442], we obtain a SD value of 2.2 for a 3-month intervention. This would correspond to detecting a difference of $1.26 \text{ mL O}_2 \cdot \text{kg}^{-1} \cdot \text{min}^{-1}$ in any comparison with 80% power, assuming a SD=2.2.

- **Aim 2:** In a similar fashion, a simplified comparison of those with gene expression below the median vs. those above the median would be able to detect a difference of $1.26 \text{ mL O}_2 \cdot \text{kg}^{-1} \cdot \text{min}^{-1}$ in peak VO₂ with 80% power. Analyses of combined training groups facilitates capacity to detect smaller differences between groups.

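### The Aim 1 power statement assumes 40 per group, but the allocation leaves 24 combined-training patients against 48, and 1RM has no calculation of its own

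*Combined protocol and SAP*

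**What the plan says.** The Aim 1 analysis takes "changes in the functional outcomes (peak VO₂, 1RM) from baseline as the continuous outcome measures in separate models". It limits testing so that "only the pre-planned comparisons of the combined aerobic-strength training to the other regimens will be considered". Combined vs aerobic on 1RM is therefore a planned Aim 1 contrast.

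Under Sample size/Power, the Aim 1 paragraph begins "For this aim, we present calculations for detecting differences in peak VO₂". It gives expected changes and an SD for that outcome alone. The only other figure there is generic: 0.64 SD at 80% power, two-sided 5%, 40 per group, by a two-sample t-test. The same section says that the calculations allow for 20% attrition.

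Strength figures appear only outside the power section. In the Background, under Strength training, a three-group trial is reported: "Strength increased in the resistance training group by 30"%, against 21% with endurance training.

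Study Population says of the 150-patient target: "This target will allow for adequate power to address the study objectives even after accounting for a 20% drop-out rate". Table 5 and the total below it give 60 aerobic, 60 IMT and 30 combined. All 30 combined patients are at Pittsburgh, alongside 35 aerobic and 35 IMT.

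**The concern.** Every Aim 1 comparison uses the combined arm, which is the smallest. A detectable effect worked out for 40 per group does not describe a contrast with 30 enrolled and 24 expected to finish.

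For 1RM there is a further gap. The plan gives no expected difference, SD of change or pre/post correlation, so even a correct figure in SD units cannot be turned into kilograms.

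Combined vs aerobic on 1RM asks whether adding strength work yields strength that aerobic training alone does not. If that contrast is described in advance as adequately powered, a non-significant result could be read as showing no added strength benefit.

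**Working it through.** **1. The plan's own figure.** Two-sample t-test, two-sided 5%, noncentral t, 40 vs 40: detectable effect 0.634 SD, and power at 0.64 SD is 80.7%. The stated 0.64 SD reproduces.

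**2. The planned allocation.** Combined 30 × 0.8 = 24; aerobic 60 × 0.8 = 48; Pittsburgh aerobic 35 × 0.8 = 28. The standard error of a difference in SD units is √(1/n₁ + 1/n₂).

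| Contrast | SE (SD units) | Detectable at 80% | Power at 0.64 SD |
|---|---|---|---|
| 40 vs 40 (as stated) | 0.224 | 0.63 SD | 81% |
| 24 vs 48 (both sites) | 0.250 | 0.71 SD | 71% |
| 24 vs 28 (Pittsburgh only) | 0.278 | 0.79 SD | 62% |

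For 24 vs 48 the noncentrality at 0.64 SD is 0.64/0.250 = 2.56 on 70 df. IMT has the same numbers as aerobic (60 in all, 35 at Pittsburgh), so the table also applies to combined vs IMT. The Pittsburgh row is the comparison among patients who could have been randomised to either arm, since Boston has no combined arm.

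**3. 1RM, as an illustration only.** The pilot gives "1RM [154.8±52.0 vs. 195.3±56.8kg, p<0.01", where the first value is for HF patients. The Background reports 30% with resistance training and 21% with endurance training, a gap of 9 points: 0.09 × 154.8 = 13.9 kg. SD of change = 52.0 × √(2(1 − r)). The documents give no r, so it is assumed.

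| Assumed r | SD of change | Detectable, 24 vs 48 (0.71 SD) | Detectable, 24 vs 28 (0.79 SD) | Power for 13.9 kg, 24 vs 48 | Power for 13.9 kg, 24 vs 28 |
|---|---|---|---|---|---|
| 0.5 | 52.0 kg | 36.9 kg | 41.1 kg | 18% | 16% |
| 0.7 | 40.3 kg | 28.6 kg | 31.8 kg | 28% | 23% |
| 0.8 | 32.9 kg | 23.4 kg | 26.0 kg | 39% | 32% |
| 0.9 | 23.3 kg | 16.5 kg | 18.4 kg | 66% | 56% |
| 0.95 | 16.4 kg | 11.6 kg | 13.0 kg | 92% | 85% |

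At 24 vs 48, 80% power for this gap needs an SD of change of at most 19.6 kg, or r of about 0.93.

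**4. A second route to the SD.** For 13 men in combined circuit training: "Significant improvements were seen in muscle strength (392 to 462 kg", P = 0.001). If that P-value comes from a paired t-test (an assumption), t on 12 df is 4.318, the SE is 70/4.318 = 16.2 kg, and the SD of change is 16.2 × √13 = 58.5 kg, or 58.5/392 = 14.9% of baseline. The 9-point gap is then 9/14.9 = 0.604 SD: power 66% at 24 vs 48, 57% at 24 vs 28. If the P-value was rounded from anywhere between 0.0005 and 0.0015, the 66% becomes 62% to 74%.

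**5. Other strength figures in the protocol.** The investigator's 10-week resistance trial in older women with HF (Preliminary Data, section 2) reports +43.4%. Set against the 21% for endurance, that is 0.224 × 154.8 = 34.7 kg, with power at 24 vs 48 of 75% at r = 0.5 and 92% at r = 0.7. The circuit-training gain is 70/392 = 17.9%, below 21%, so on that figure there is no advantage to detect.

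**The case against.** **The general statement covers any outcome.** It is in SD units, so it could serve for 1RM. The enrolled 30 vs 60 also carries the same information as 40 per group (2 × 30 × 60/90 = 40). Both points are right, but the second holds only with no drop-out. The power section says that 20% attrition is built in, and Study Population claims adequacy after it. The first does not help a reader who has no SD of 1RM change.

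**The sample size may be 210.** The power section still mentions 210 recruits and four arms; 210 × 0.8/4 = 42, close to 40 per group. That may be where the figure comes from, but the only allocation by arm is the one for 150.

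**The plan does not lean on single tests.** General considerations puts the weight on overall results. This softens the consequence of one null contrast but does not correct the power statement.

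**Stronger readings that the documents do not support.** A reader might infer that power on 1RM is at most about 66%. It is not a ceiling: a correlation of 0.95 or the 43.4% gain gives much more. Nor are the source measures shown to be leg-press 1RM. The 30% vs 21% trial tested knee and elbow muscles, and the 392 kg baseline is about 2.5 times the pilot 1RM.

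A reader might also take 9 points as the most that combined training could gain over aerobic, because only half of each session is strength work. But the Background describes synergy when the two are combined and credits endurance training itself with 21%.

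Finally, one might infer that combined vs IMT on 1RM is almost sure to be significant, so that the pattern of results would reflect power. That assumes IMT has no effect on strength, whereas the Background links IMT to better strength capacity and likens it to strength training.

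**Conclusion.** The concern holds in this form. With Table 5 and 20% attrition, combined-arm contrasts detect 0.71 SD at 80% power (0.79 SD within Pittsburgh), not 0.64 SD, and power at 0.64 SD is about 71% (62% within Pittsburgh). This rests only on the plan's own numbers and its simplified t-test.

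For 1RM, adequate power is not shown. This is not a finding that power is low by any particular amount: the cited strength figures run from no expected advantage to high power, and the pre/post correlation is unknown. The statement that 1RM has no calculation of its own applies to the text available, which lacks a portion just before the statistical section.

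**What to change.** In Sample size/Power, replace the 40-per-group figure for combined-arm contrasts with 0.71 SD for 24 vs 48, and give 0.79 SD for the Pittsburgh-only comparison. For peak VO2 with the plan's SD of 2.2, 0.71 SD is 0.71 × 2.2 = 1.56 mL·kg⁻¹·min⁻¹. For 1RM, express it over a range of assumed SDs of change, for example 11.6 kg to 36.9 kg for correlations of 0.95 down to 0.5, and label the correlations as assumptions.

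In Study Population, restrict the adequate-power sentence so that it no longer covers the combined-arm contrasts, 1RM included, without qualification.

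In Aim 1, say that combined vs aerobic on 1RM will be reported as an estimate with a 95% CI, and that non-significance will not be read as absence of added strength benefit.

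The cost is wording in three places and no extra patients. The stated power becomes less favourable.

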Analyses of gene expression in relation to functional capacity also show several key correlations between generally suppressed in atrophying muscle and generally suppressed aerobic capacity in HF patients. PGC-1 α correlated with peak VO₂ ($r=0.49$, $p<0.05$) and P_{ET}CO₂ ($r=0.43$, $p<0.05$). IGFBP5 correlated with peak VO₂ ($r=0.60$, $p<0.01$), the VE/VCO₂ slope ($r=-0.44$, $p<0.05$), and P_{ET}CO₂ ($r=0.52$, $p<0.01$), and approached significance with peak VE/VO₂ ($r=-0.40$, $p=0.053$). There were significant correlations between expression of genes induced in atrophying muscle and function. Peak VO₂ correlated with MURF-1 ($r=-0.42$, $p<0.05$), FoxO1 ($r=-0.50$, $p<0.01$), FoxO3 ($r=-0.52$, $p<0.01$), and GLUL ($r=-0.36$, $p<0.05$). P_{ET}CO₂ correlated with atrogin-1 ($r=-0.38$, $p<0.05$) and MURF-1 ($r=-0.38$, $p<0.05$). GLUL correlated with 1RM ($r=-0.37$, $p<0.05$) and sub-maximal power ($r=-0.36$, $p<0.05$). These data provide strong rationale for further analysis of atrophy-associated gene expression in skeletal muscle following a tailored exercise intervention.

Table 2: Abstracts submitted to the Am College of Cardiology, 2012 reflecting phase II analysis:

PGC-1 α and IGFBP-5 Expression in Skeletal Muscle of HF patients	PGC-1 α and IGFBP-5 expression in skeletal muscle correlate with CPX and strength indices of physical function.
Gene Expression of the Ubiquitin-Proteasome Pathway is reflected by Ventilatory Expired Gas Analysis Indices at Peak Exercise in Heart Failure	FoxO1 and FoxO3 expression correlates with reduced aerobic and strength parameters
Correlations between Recovery Kinetics and Skeletal Muscle Gene Expression in Systolic Heart Failure	Skeletal muscle atrophy-associated gene expression patterns (Atrogin-1, MURF-1, FoxO1 and FoxO3) in controls correlate with delayed VO ₂ recovery kinetics, while anabolic PGC-1 α , IgF1 and IgF-binding protein-5 were associated with increased VO ₂ .

2. Prior work in exercise training and exercise testing for heart failure patients

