[name] not only led the exercise testing, training, and organization for HF-ACTION, but was then selected as lead writer on the HF-ACTION baseline data paper focused on older HF patients, showing important age-related covariates contributing (but not entirely explaining) age-related changes in CPX performance. Age was the strongest predictor of peak VO₂ and the VE/VCO₂ slope in this population of HF patients (accounting for 13% of the variability in peak VO₂ and 4% of the VE/VCO₂ slope after controlling for other variables in the model). BMI, sex, race, and NYHA classification were also independent predictors of peak VO₂; when added to age they accounted for 39% of the variability. Furthermore, adding peak HR increased R² from 0.392 to 0.494. Age-related effects were nonlinear and showed splines at age 40 years for peak VO₂ and age 70 years for the VE/VCO₂ slope. These effects do not appear to be mediated via age-related increases in comorbidities (86).

[name] also recently completed a study (presented at the AHA, 2011; manuscript in submission) of the 6MWT completed by enrollees in HF-ACTION in comparison to the CPX data, assessing their relative utility as prognostic gauges. 6MWT distance correlated significantly with peak VO₂ and the VE/VCO₂ slope: unadjusted $r = 0.537$, -0.259 and adjusted $r = 0.333$, -0.176 ($p<0.0001$ in all). Moreover, using C-indices 6MWT distance predicted hospitalization/death and death (unadjusted and adjusted) with similar efficacy to peak VO₂ and the VE/VCO₂ slope (Table 3).

Table 3: C-indices to Compare Risk Prediction between 6MWD and CPX

	All-cause Hospitalization/Death		All-cause Death	
	Unadjusted	Adjusted	Unadjusted	Adjusted
6MWT	0.581	0.620	0.650	0.722
Peak VO ₂	0.606	0.630	0.682	0.733
VE/VCO ₂ slope	0.561	0.606	0.647	0.708

While still working on HF-ACTION, [name] collaborated with [name] and [name] in the NCCAM Trial Tai Chi Mind-Body Movement Therapy for Patients with Chronic HF. [name] completed all CPX for that study, which showed that tai chi (TC) improved quality of life, mood, and exercise self-efficacy in patients with HF as compared to a matched attention control population (87).

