General considerations: The analyses described below are of continuous outcome measures, primarily changes in function outcomes and gene expression and either continuous or categorical predictors. All analyses will be performed as general linear models. Potential confounders of each analysis will be outlined below and a 10% rule for evaluating confounders will be used, namely including a potential confounder if a 10% or greater change is seen in the main predictor effect. In all instances, outcome variables will be evaluated for violation of regression assumptions and transformation of these variables will be considered as a remedy if needed. Analyses will generally be performed with an intent-to-treat approach, with sensitivity analyses performed to assess the role of drop-outs on the results.

This grant examines a complex interplay of exercise regimens, gene expression and functional measures, resulting in a number of hypotheses that require testing. We are cognizant of the role of type I error in this and in interpreting results, focus will be placed on the overall results of these analyses and not on the results of individual tests. Thus, for example, significant relationships among gene expression outcomes and treatment categories as a whole will be considered as support for these hypotheses and isolated significant associations will not be unduly weighted in the interpretation of results.

Randomization will be generated using a SAS program based upon permuted random blocks of variable size to assure approximate balance over time and will be stratified by sex and statin use.

Validation of Study Measurements: At the start of the study, there will be two assessments of physical function battery. Intraclass correlations will be used to determine the relative repeatability of the various components of the battery. This information will be included in all manuscripts using these measures.

- *Aim 1. To assess differences in functional outcomes (peak VO₂, 1RM) relative to the training therapy:*

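### The Aim 2 gene-to-function models omit baseline function, so the two change scores can correlate in the hypothesised direction without any mechanism if each change depends on its own baseline

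*Combined protocol and SAP*

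**What the plan says.** The Aim 2 paragraph of the statistical text takes changes in proteolytic (FoxO, ubiquitin) and anti-proteolytic (IGF-1, PGC-1α) gene expression "as predictors of the change in functional outcomes", with peak VO2 and 1RM in separate linear models. Each model has "gene expression changes as the primary predictor and the following variables considered as potential confounders: age, sex, and comorbidities". Under General considerations, the entry rule is "including a potential confounder if a 10% or greater change is seen in the main predictor effect". Neither place names the baseline value of the outcome or of the gene as a model term.

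Two other sections point to a wider set. Effects of Confounders says that height, weight, medications and other clinical parameters will be considered in the functional assessments. The Exclusion Criteria say that statin use will be factored into the analysis. Neither names baseline function or baseline expression as a covariate.

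The pilot results (Preliminary Data, Phase II) state: "There were significant correlations between expression of genes induced in atrophying muscle and function". For peak VO2 in HF patients they give r = -0.52 for FoxO3, -0.50 for FoxO1 and +0.49 for PGC-1α.

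**The concern.** Gene change is not randomised, so randomisation does not protect this model. The pilot suggests that less fit patients start with higher FoxO and lower PGC-1α. Suppose that less fit patients gain more VO2, and that patients with the most abnormal expression move furthest back. FoxO then falls where VO2 rises, and PGC-1α rises where VO2 rises, even if neither affects the other. That is the pattern Aim 2 would read as support for its mechanism.

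The plan's general safeguard is to weigh results as a whole rather than singly. It does not help against a bias that moves several correlated genes the same way. The Limitations section answers confounding mainly with a larger sample, but a larger sample makes a biased association more significant.

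**Working it through.** **The plan's own Aim 2 figure.** The stated detectable difference is 1.26 with SD 2.2, two-sided 5%, 80% power. 1.26/2.2 = 0.573 SD, and n = 2(1.96 + 0.842)²/0.573² ≈ 48 per group. The figure reproduces at 48 per group, which is an arm of 60 less 20%. It is a power statement and says nothing about confounding.

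**Inputs from the documents**
- Baseline r0 = -0.52, FoxO3 with peak VO2 (Phase II).
- SD of peak VO2 in HF patients, 4.2 (Phase I).
- SD of change in peak VO2, 2.2 (Sample size, Aim 1).
- n = 150 × 0.8 = 120. The Sample size text says 210, which gives 168.

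**Assumptions (no figures in the documents)**
- VO2 gain falls by b per unit of baseline VO2, b = 0.10 to 0.25.
- Gene change falls by d per unit of baseline expression, d = 0.4 to 0.6.
- For the hand calculation, the SD of gene change equals the SD of baseline expression.
- There is no true link between the two changes.

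**Formula.** Spurious r = r0 × (b × 4.2/2.2) × d. The false-positive rate is Φ(z - 1.96) + Φ(-z - 1.96), with z = atanh(|r|) × √117.

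| b | d | b × 4.2/2.2 | spurious r | false-positive rate |
|---|---|---|---|---|
| 0.10 | 0.4 | 0.191 | -0.040 | 7% |
| 0.10 | 0.6 | 0.191 | -0.060 | 10% |
| 0.15 | 0.4 | 0.286 | -0.060 | 10% |
| 0.15 | 0.6 | 0.286 | -0.089 | 16% |
| 0.25 | 0.4 | 0.477 | -0.099 | 19% |
| 0.25 | 0.6 | 0.477 | -0.149 | 37% |

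Simulation with measurement error added gives about 7-39% over the same range. If b or d is zero, the product is zero and the rate is 5%. For PGC-1α, r is smaller by 0.49/0.52 and positive, which is again the hypothesised sign. Sample size makes it worse: if each change has a correlation of -0.5 with its own baseline, r = -0.52 × 0.25 = -0.13 and the rate is 29% at n = 120 and 39% at n = 168.

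**What adjustment does (simulation, n = 120)**
- *Baseline function only.* Total rejection is 10% or less in every setting run, and false positives in the hypothesised direction are 3% or less. What excess remains runs against the hypothesis. Measurement error leaves some true fitness unadjusted, and fitter patients have less FoxO to lose.
- *Both baselines.* If baseline dependence is measurement error alone, the unadjusted model holds 5%, but this model gives about 8-16% at assumed reliabilities (peak VO2/gene) of 0.93/0.8 to 0.88/0.5. At the noisier settings almost all of it is in the hypothesised direction.

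The VO2 reliabilities are possible on the documents' figures: with SDs of 4.2 and 2.2, the lowest is 1 - 2.2²/(2 × 4.2²) = 0.86.

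**The case against.** The strongest reply is that the bias is conditional and has not been shown. The pilot correlations are cross-sectional and say nothing about change. At b = 0.10 the rate is only 7-10%; the upper end needs b = 0.25, which no document supports. This stands, and it limits the claim. A reader might infer that the spurious link always arises, or that baseline severity is an established common cause. The documents support neither.

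A second reply concerns the remedy. It is tempting to think that forcing in both baselines restores 5% in every case. It does not: with a noisy assay that model can produce the false link itself. The mRNA extraction and rtPCR section reports poor precision in the pilot when samples were spread over several plates, and this trial batches by exercise arm. So the two-baseline model belongs among the sensitivity analyses.

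A reader might also infer that the confounder list is closed, or that NYHA class and BMI must be added. Effects of Confounders and the Exclusion Criteria already mention weight, medications and statins, so the sections need reconciling. The HF-ACTION baseline work does say "BMI, sex, race, and NYHA classification were also independent predictors" of peak VO2, but that concerns its level, not its change, and no passage links either variable to gene expression.

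The evidence is also narrower than Aim 2. No pilot correlation with peak VO2 is given for ubiquitin or IGF-1. For 1RM the only r given is for GLUL, which Aim 2 does not name.

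**Conclusion.** The concern holds in a limited form. The Aim 2 gene-to-function models have no term for baseline function, and for FoxO and PGC-1α the pilot correlations have the sign that would turn baseline dependence into apparent support for the mechanism. The size is about 7-39% false positives per gene test at n = 120, against a nominal 5%. That rests on assumed b = 0.10-0.25 and d = 0.4-0.6, on both dependences being present, and on the pilot r and the two SDs carrying over to this trial. If either dependence is absent there is no inflation. The figures are for peak VO2 only; nothing comparable can be computed for 1RM. This is a cheap improvement to prespecify, not a demonstrated bias.

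**What to change.** In the Aim 2 paragraph:
- Force the baseline value of the functional outcome into each gene-to-function model, exempt from the 10% rule. Use the mean of the two baseline tests described under Validation of Study Measurements where both are available.
- Report two sensitivity analyses: the model without baseline, and the model that also adds baseline expression of the gene. State in advance that the second can create a link when baselines are noisy.
- Describe the result as an association.
- Reconcile the covariate list with Effects of Confounders and the statin statement in the Exclusion Criteria. NYHA class and BMI may join as candidate confounders, but they are not shown to be needed.

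The cost is a change of wording and one degree of freedom per model, using data already planned. The estimate may be less favourable and have less power where the unadjusted association was inflated by baseline. With weak dependence on baseline VO2 and a noisy assay, the total false-positive rate may be no lower than without adjustment, although the excess then runs against the hypothesis.
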